11.3 Other response parameters

Progression-free survival (PFS) and overall survival (OS) will be recorded from start of study to progression or death (PFS), or time from start of study to death (OS).

12. STUDY OVERSIGHT AND DATA REPORTING /REGULATORY REQUIREMENTS

Adverse event lists, guidelines, and instructions for AE reporting can be found in Section 7.0 (Adverse Events: List and Reporting Requirements).

12.1 Study Oversight

This protocol is monitored at several levels, as described in this section. The Protocol Principal Investigator is responsible for monitoring the conduct and progress of the clinical trial, including the ongoing review of accrual, patient-specific clinical and laboratory data, and routine and serious adverse events; reporting of expedited adverse events; and accumulation of reported adverse events from other trials testing the same drug(s). The Protocol Principal Investigator and statistician have access to the data at all times through the CTMS web-based reporting portal.

For the Phase 1 portion of this study, all decisions regarding dose escalation/expansion/de-escalation require sign-off by the Protocol Principal Investigator through the CTMS/IWRS. In addition, for the Phase 1 portion, the Protocol Principal Investigator will have at least monthly,

or more frequently, conference calls with the Study Investigators and the CTEP Medical Officer(s) to review accrual, progress, and adverse events and unanticipated problems.

All Study Investigators at participating sites who register/enroll patients on a given protocol are responsible for timely submission of data via Medidata Rave and timely reporting of adverse events for that particular study. This includes timely review of data collected on the electronic CRFs submitted via Medidata Rave.

All studies are also reviewed in accordance with the enrolling institution's data safety monitoring plan.

There are two safety/stopping rules included in this clinical trial:

Stopping rule 1: Delayed immune related toxicity from dose escalation phase. If 4 or more patients in any dose level develop delayed protocol defined immune related grade 3/4 events, we will halt further therapy on that dose level

Stopping rule 2: Excess toxicity in the expansion cohort. We will cease enrollment in the expansion phase at the dose determined from the dose escalation part of the study if we observe two or more DLTs among the first six evaluable patients enrolled in the expansion cohort. An evaluable patient is any patient who received a study drug. If the true toxicity rate is 50% or greater at the MTD then this rule will stop the trial with probability at least .89. Similarly, if the true toxicity rate is 33% at the MTD then this stopping rule will end the trial with probability .65. In that event, a new expansion cohort will start at the dose level immediately below the dose level that was expanded. If the dose level being expanded is dose level -1, then the study will be terminated.

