We will perform '3+3' classical dose escalation design to determine DLT. The first 3 patients will receive ENT at dose level 1 (DL1: 8mg on D1, 8 of 21-day cycles). pembrolizumab (MK-3475) will be added starting day 1 cycle 2 at the approved dose (200mg intravenously [IV] over 30 minutes on D1 of 21-day cycles) for 4 cycles. A safety committee that includes the study chair, the principal investigator from any study site that has enrolled a patient on the specific DL, as well as two sub-investigators from Yale will review safety data after enrollment of every 3 patients during the dose escalation phase. The committee will have the discretion to decide to enroll 3 more patients in the specific dose level even if no DLT occurred in the first 3 treated patients in that dose level if there are toxicity/safety concerns that did not qualify as DLT (maximum of 6 evaluable patients to be enrolled at any dose level). The committee can also decide to enroll patients at a lower dose level after the first 3 or after the first 6 patients enrolled in any dose level even if no or one DLT occurred at that dose level if there are toxicity/safety concerns that did not qualify as DLT. The following regarding enrollment in different dose levels will be considered guidance for the safety committee but can be modified in accordance of above: If no patient of the 3 patients treated with combined therapy at DL1 develops DLT, then dose level 2 (DL2) will be tested. DL2 will be with ENT at 8mg on D1, 8 and 15 and pembrolizumab (MK-3475) at 200mg IV on D1 of 21-day cycles. If 1 patient out of the 3 patients has DLT at DL1, we will expand cohort to 3 more patients and if 1 patient of the 6 patients has DLT (i.e. only 0/3 or 1/6), we will test next dose (DL2). If no patient of the 3 patients treated with combined therapy at DL2 develop DLT, then DL2 will be used for part 2 (expansion cohort). If 1 patient out of the 3 patients has DLT at DL2, we will expand cohort to 3 more patients and if 1 patient of the 6 patients has DLT (i.e. only 0/3 or 1/6), dose level 2 (DL2) will be used for part 2 (expansion cohort). If 2 patients or more of the 6 patients at DL2 experience DLT, DL1 will be used for expansion cohort. The cycle duration will be 21 days, the maximum number of treatment cycles of entinostat will be 18 cycles and for pembrolizumab (MK-3475) the maximum number of cycles will be 17. Cycle 2 to cycle 18, will have concurrent administration. In all the phases of the study, entinostat will be administered in clinic within 2 hours before administration of pembrolizumab (MK-3475). Entinostat will be stored at the pharmacy and it will not be given for the patient to take home.

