A safety committee that includes the study chair, the principal investigator from any study site that has enrolled a patient on the specific DL, as well as two sub-investigators from Yale will review safety data after enrollment of every 3 patients during the dose escalation phase. The committee will have the discretion to decide to enroll 3 more patients in the specific dose level even if no DLT occurred in the first 3 treated patients in that dose level if there are toxicity/safety concerns that did not qualify as DLT (maximum of 6 evaluable patients to be enrolled at any dose level). The committee can also decide to enroll patients at a lower dose level after the first 3 or after the first 6 patients enrolled in any dose level even if no or one DLT occurred at that dose level if there are toxicity/safety concerns that did not qualify as DLT. The following regarding enrollment in different dose levels will be considered guidance for the safety committee but can be modified in accordance of above. Dose escalation will proceed within each cohort according to the following scheme.

Number of Patients with DLT at a Given Dose Level	Escalation Decision Rule
0 out of 3	Enter 3 patients at the next dose level.
≥ 2	Dose escalation will be stopped. This dose level will be declared the maximally administered dose (highest dose administered). Three (3) additional patients will be entered at the next lowest dose level if only 3 patients

	were treated previously at that dose.
1 out of 3	
Enter at least 3 more patients at this dose level.
 
• If 0 of these 3 patients experience DLT, proceed to the next dose level.• If 1 or more of this group suffer DLT, then dose escalation is stopped, and this dose is declared the maximally administered dose. Three (3) additional patients will be entered at the next lowest dose level if only 3 patients were treated previously at that dose.
≤ 1 out of 6 at highest dose level below the maximally administered dose	This is generally the recommended phase 2 dose (RP2D)= MTD. At least 6 patients must be entered at the recommended phase 2 dose (RP2D).

Management and dose modifications associated with the above adverse events are outlined in [Section 6](#).

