We will perform '3+3' classical dose escalation design to determine dose limiting toxicity (DLT). The first 3 patients will receive ENT at dose level 1 (DL1: 8mg on D1, 8 of 21-day cycles). Pembrolizumab (MK-3475) will be added starting day 1 cycle 2 at the approved dose of 200mg intravenously [IV] over 30 minutes on D1 of 21-day cycles for 4 cycles. A safety committee that includes the study chair, the principal investigator from any study site that has enrolled a patient on the specific DL, as well as two sub-investigators from Yale will review safety data after enrollment of every 3 patients during the dose escalation phase. The committee will have the discretion to decide to enroll 3 more patients in the specific dose level even if no DLT occurred in the first 3 treated patients in that dose level if there are toxicity/safety concerns that did not qualify as DLT (maximum of 6 evaluable patients to be enrolled at any dose level). The committee can also decide to enroll patients at a lower dose level after the first 3 or after the first 6 patients enrolled in any dose level even if no or one DLT occurred at that dose level if there are toxicity/safety concerns that did not qualify as DLT. The following regarding enrollment in different dose levels will be considered guidance for the safety committee but can be modified in accordance of above: If no patient of the 3 patients treated with combined therapy at DL1 develops DLT, then dose level 2 (DL2) will be tested. For instance, DL2 will be with ENT at 8mg on D1, 8 and 15 and MK-3475 (pembrolizumab) at 200mg IV on D1 of 21-day cycles. If 1 patient out of the 3 patients has DLT at DL1, we will expand cohort to 3 more patients and if 1 patient of the 6 patients has DLT (i.e. only 0/3 or 1/6), we will test next dose (DL2). If no patient of the 3 patients treated with combined therapy at DL2 develop DLT, then DL2 will be used for part 2 (expansion cohort). If 1 patient out of the 3 patients has DLT at DL2, we will expand cohort to 3 more patients and if 1 patient of the 6 patients has DLT (i.e only 0/3 or 1/6), dose level 2

(DL2) will be used for part 2 (expansion cohort). If 2 or more patients of the 6 patients have DLT, DL1 will be used for expansion cohort.

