13.2 Sample Size/Accrual Rate

We expect to accrue 1-2 patients with MDS per month once the study is open.

Currently there is no therapy that has been shown to prolong survival in MDS in the post-DNMTi setting and that the expected best response in patients receiving supportive care only in post-DNMTi setting is negligible (1% or less). It is generally accepted that a $\geq 15\%$ ORR in the post-DNMTi is clinically meaningful and would be worth further evaluation in larger studies.

The total number of patients enrolled in the study will range from 21 to 27. The null hypothesis response rate of 1% (only supportive care) will be rejected if we observe 2 or more favorable responses. These criterion has significance level between .02 and .03 using a one-sided binomial test. This criterion has power between .84 and .93 for testing an alternative response rate of 15% with the combination therapy. Therefore, we will treat a total of 21 patients in the combination arm (6 in the first part of the study and 15 in the second part of the study).

DOMESTIC PLANNED ENROLLMENT REPORT						
Racial Categories	Ethnic Categories				Total	
	Not Hispanic or Latino		Hispanic or Latino			
	Female	Male	Female	Male		
American Indian/ Alaska Native	1	1	1	1	4	
Asian	1	1	0	0	2	
Native Hawaiian or Other Pacific Islander	1	0	0	0	1	
Black or African American	1	1	1	1	4	
White	4	4	1	1	10	
More Than One Race	0	0	0	0		
Total	8	7	3	3	21	

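### Stopping rule 1 cannot fire at an escalation level left at 3 patients and needs 4 of 6 at the cap, and its wording leaves unclear whether expansion patients count

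*Combined protocol and SAP*

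**What the plan says.** Section 12.1 lists two stopping rules. The first is headed "Delayed immune related toxicity from dose escalation phase". Its trigger is "If 4 or more patients in any dose level develop delayed protocol defined immune related grade 3/4 events", and its action is "we will halt further therapy on that dose level". It gives no denominator, no time window and no operating characteristics.

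The second rule is headed "Stopping rule 2: Excess toxicity in the expansion cohort". It stops enrolment at two or more DLTs among the first six expansion patients, and it states stopping probabilities of at least .89 at a true rate of 50% and .65 at 33%.

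On cohort size, the synopsis and Sections 5.1, 5.2 and 13.1 enter 3 patients at a level and leave DL1 at 3 after 0/3 DLTs. A level grows to 6 after one DLT in 3 or if the safety committee so decides, with a "maximum of 6 evaluable patients to be enrolled at any dose level". Section 5.2 replaces patients who do not complete two combined cycles.

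For the dose carried forward the text diverges. Section 13.1 says "If no patient of the 3 patients treated with combined therapy at DL2 develop DLT, then DL2 will be used for part 2". The escalation table in Section 5.2 says "At least 6 patients must be entered at the recommended phase 2 dose (RP2D", and Section 13.2 plans "6 in the first part of the study and 15 in the second part of the study".

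**The concern.** The DLT window covers two combined cycles, while combined treatment can run to 17. Section 6.2.1 warns that immune events may appear months after the last dose. Rule 1 is the only cohort-level rule with a number attached to immune toxicity after the DLT window. Its threshold exceeds the standard cohort size, so at a level left at 3 patients it is listed as a safeguard but cannot act. At 6 it acts only when most of the cohort is affected. An oversight body reading Section 12.1 could take more assurance from the rule than it gives.

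**Working it through.** **Inputs.** The threshold is 4 patients (Section 12.1). Escalation sizes are 3, or up to 6 evaluable (Sections 5.2 and 13.1), and the expansion adds 15 (Section 5.3). Delayed is taken to mean after the two-cycle DLT window, because the plan does not define it. The documents give no delayed-event rate for this combination, so all rates below are assumptions; 33% and 50% are the rates that rule 2 uses for DLTs. Patients are treated as independent, and 33% is computed as 1/3.

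**Rule 2, to check the method.** P(at least 2 of 6) = 1 − (1−p)^6 − 6p(1−p)^5.
- p = 1/2: 1 − 7/64 = .891 (plan: at least .89).
- p = 1/3: 1 − 256/729 = .649 (plan: .65).

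The plan's figures reproduce.

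**Rule 1, escalation patients only.** At 3 patients four events are impossible, so the probability is 0 at any rate. At 6 the rule needs 4/6 = 67%, and P(at least 4 of 6) = 15p^4(1−p)^2 + 6p^5(1−p) + p^6.
- p = 1/3: (60 + 12 + 1)/729 = .100.
- p = 1/2: (15 + 6 + 1)/64 = .344.

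**All sizes, same threshold of 4.**

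| Patients counted | Share needed | 10% | 20% | 33% | 50% |
|---|---|---|---|---|---|
| 3 | not attainable | 0 | 0 | 0 | 0 |
| 4 | 100% | .0001 | .002 | .012 | .063 |
| 6 | 67% | .001 | .017 | .10 | .34 |
| 7 | 57% | .003 | .033 | .17 | .50 |
| 8 | 50% | .005 | .056 | .26 | .64 |
| 21 (6 + 15) | 19% | .15 | .63 | .95 | >.99 |

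The row for 4 is a 3-patient cohort with one replacement. The rows for 7 and 8 are an assumed range for a 6-patient level with replacements. At 6 the true rate must reach 58% before the rule fires half the time.

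Incomplete follow-up works the other way. If only half of each patient's delayed-event risk were observed (an assumption), the 33% and 50% figures at 6 would fall to .009 and .04.

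**Illustrative replacement: at least 2 of the first 3, otherwise at least 3 of 6.**
- 10%: .028 + .243 × .028 + .729 × .001 = .036.
- 20%: .104 + .384 × .104 + .512 × .008 = .148.
- 33% and 50%: .39 and .70 by the same formula.
- A level that stays at 3 halts with .028 at 10% and .104 at 20%, against 0 now.

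**The case against.** Four arguments count against the concern.

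- **Scope.** The trigger speaks of patients in any dose level, and the action applies to that same level. If a dose level includes its expansion patients, the rule is 4 of 21 and quite responsive. The heading, and the separate rule for expansion, favour counting escalation patients only. The pooled reading cannot be excluded, though, and the two readings give .10 and .95 at a 33% rate. That gap is itself a reason to clarify.
- **The cap.** It limits evaluable patients, while rule 1 counts patients, and Sections 11.1 and 13.5.1 make all treated patients evaluable for toxicity. The 67% therefore softens to 57% or 50% with one or two replacements. This stands in part, since patients who leave early may contribute few delayed events.
- **A deliberate high bar.** Rule 1 withdraws therapy where the synopsis says there is no standard of care. The DLT table stops escalation and rule 2 stops enrolment, so neither is a strict benchmark. A demanding threshold is legitimate, but this does not explain one that a 3-patient level cannot reach.
- **Other protection.** Section 5.5 and the Section 6.2.3 tables govern individual holding and discontinuation. Sections 5.1 and 13.1 schedule a safety assessment after five cycles (the synopsis places it at the end of the DLT period). The safety committee has discretion, Section 12.1 requires at least monthly calls, and Section 14.1 has closure provisions. These stand as mitigation, although none sets a count.

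A reader might infer that the trial has no control on late immune toxicity. The safeguards just listed contradict that. A reader might also infer that the rule is dead at the dose taken to expansion. That follows only if Section 13.1's 0/3 path is used despite the minimum of 6 in Section 5.2. Under Section 5.2, the 3-patient case is mainly a level escalated past, such as DL1 after 0/3. Where patients with events have already been discontinued, a halt there after 2 of 3 protects one remaining patient.

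**Conclusion.** The concern holds for the rule read as its heading directs. With escalation patients only, rule 1 cannot fire at a level that stays at 3. At 6 evaluable patients it misses a true 33% rate nine times in ten and a true 50% rate about two times in three. With 7 or 8 treated it remains weak at 33%. If expansion patients count, the rule behaves quite differently, so its protection depends on a scope the text leaves unclear.

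The impossibility at 3 and the 67% at 6 need no assumed event rate. The probabilities rest on assumed rates, independence and full observation of delayed events. Severity is minor: this is a gap in one formal rule, with other safeguards around it.

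**What to change.** Restate rule 1 as a count for each number treated that can be met at every escalation size, for example at least 2 of 3 and at least 3 of 6. The sponsor and safety committee should set the final numbers. Say in the same sentence whether only escalation patients count. If expansion patients at that dose count too, give a separate threshold for the pooled number: 21, or 18 only if the 3 + 15 path stands. It would also help to define delayed as after the two-cycle DLT window.

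A flat threshold of 3 at either size does not remedy the 3-patient case. Three of 3 leaves nobody at that level to protect unless the dose is being expanded.

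The change is a wording amendment with no extra patients or visits. Its cost is more false halts. For a level growing from 3 to 6, the example raises the halt probability from .001 to .036 at a true 10% and from .017 to .148 at 20%. A sponsor who finds that too high can choose stricter counts, provided they can be reached.

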12.2 Data Reporting

Data collection for this study will be done exclusively through Medidata Rave. Access to the trial in Rave is granted through the iMedidata application to all persons with the appropriate roles assigned in the Regulatory Support System (RSS). To access Rave via iMedidata, the site user must have an active CTEP IAM account (check at <<https://ctepcore.nci.nih.gov/iam>>) and the appropriate Rave role (Rave CRA, Read-Only, CRA (Lab Admin, SLA or Site Investigator) on either the LPO or participating organization roster at the enrolling site. To hold Rave CRA role or CRA Lab Admin role, the user must hold a minimum of an AP registration type. To hold the Rave Site Investigator role, the individual must be registered as an NPIVR or IVR. Associates can hold read-only roles in Rave.

Upon initial site registration approval for the study in RSS, all persons with Rave roles assigned on the appropriate roster will be sent a study invitation e-mail from iMedidata. To accept the invitation, site users must log into the Select Login (<https://login.imedidata.com/selectlogin>) using their CTEP-IAM user name and password, and click on the "accept" link in the upper right-corner of the iMedidata page. Please note, site users will not be able to access the study in Rave until all required Medidata and study specific trainings are completed. Trainings will be in the form of electronic learnings (eLearnings), and can be accessed by clicking on the link in the upper right pane of the iMedidata screen.

Users that have not previously activated their iMedidata/Rave account at the time of initial site registration approval for the study in RSS will also receive a separate invitation from iMedidata to activate their account. Account activation instructions are located on the CTSU website, Rave tab under the Rave resource materials (Medidata Account Activation and Study Invitation Acceptance). Additional information on iMedidata/Rave is available on the CTSU members' website under the Rave tab or by contacting the CTSU Help Desk at [name] or by e-mail at [contact].

12.2.1 Method

CTMS Routine Monitoring:

This study will be monitored by the Clinical Trials Monitoring Service (CTMS). Data will be submitted to CTMS at least once every two weeks via Medidata Rave (or other modality if approved by CTEP). Information on CTMS reporting is available at <http://www.theradex.com/clinicalTechnologies/?National-Cancer-Institute-NCI-11>. On-site audits will be conducted on an 18-36 month basis as part of routine cancer center site visits. More frequent audits may be conducted if warranted by accrual or due to concerns regarding data quality or timely submission. For CTMS monitored studies, after users have activated their accounts, please contact the Theradex Help Desk at [contact] or by email at [contact] for additional support with Rave and completion of CRFs.

12.2.2 Responsibility for Data Submission

For ETCTN trials, it is the responsibility of the PI(s) at the site to ensure that all investigators at the ETCTN Sites understand the procedures for data submission for each ETCTN protocol and that protocol specified data are submitted accurately and in a timely manner to the CTMS via the electronic data capture system, Medidata Rave.

Data are to be submitted via Medidata Rave to CTMS on a real-time basis, but no less than once every 2 weeks. The timeliness of data submissions and timeliness in resolving data queries will be tracked by CTMS. Metrics for timeliness will be followed and assessed on a quarterly basis. For the purpose of Institutional Performance Monitoring, data will be considered delinquent if it is greater than 4 weeks past due.

Data from Medidata Rave and CTEP-AERS is reviewed by the CTMS on an ongoing basis as data is received. Queries will be issued by CTMS directly within Rave. The queries will appear on the Task Summary Tab within Rave for the CRA at the ETCTN to resolve. Monthly web-based reports are posted for review by the Drug Monitors in the IDB, CTEP. Onsite audits will be conducted by the CTMS to ensure compliance with regulatory requirements, GCP, and NCI policies and procedures with the overarching goal of ensuring the integrity of data generated from NCI-sponsored clinical trials, as described in the ETCTN Program Guidelines, which may be found on the CTEP (http://ctep.cancer.gov/protocolDevelopment/electronic_applications/adverse_events.htm

) and CTSU websites.

An End of Study CRF is to be completed by the PI, and is to include a summary of study endpoints not otherwise captured in the database, such as (for phase 1 trials) the recommended phase 2 dose (RP2D), and a description of any dose-limiting toxicities (DLTs). CTMS will utilize a core set of eCRFs that are Cancer Data Standards Registry and Repository (caDSR) compliant (<http://cbiit.nci.nih.gov/ncip/biomedical-informatics-resources/interoperability-and-semantics/metadata-and-models>). Customized eCRFs will be included when appropriate to meet unique study requirements. The PI is encouraged to review the eCRFs, working closely with CTMS to ensure prospectively that all required items are appropriately captured in the eCRFs prior to study activation. CTMS will prepare the eCRFs with built-in edit checks to the extent possible to promote data integrity.

CDUS data submissions for ETCTN trials activated after March 1, 2014, will be carried out by the CTMS contractor, Theradex. CDUS submissions are performed by Theradex on a monthly basis. The trial's lead institution is responsible for timely submission to CTMS via Rave, as above.

Further information on data submission procedures can be found in the ETCTN Program Guidelines (http://ctep.cancer.gov/protocolDevelopment/electronic_applications/adverse_events.htm).

